## 4.2.4 Rationale for Endpoints

### 4.2.4.1 Efficacy Endpoints

**Primary Endpoint:** Response Rate is a widely used and accepted marker of activity, and especially in a setting of prior PD-1/PD-L1 treatment failure is expected to be a robust outcome measure. For immunotherapy agents generally speaking response rate may underestimate the benefit (namely survival) as many patients with stable disease still achieve improved or prolonged survival.

**Secondary Endpoint:** Overall Survival (e.g. 1-year overall survival is an acceptable early outcome measure to estimate survival in a poor prognosis patient population with an estimate median overall survival of  $\leq 6$  months and  $\sim 30\%$  of patients alive at one year (*Stewart 2009*)).

### 4.2.4.2 Biomarker Research

In an effort to identify those patients who may be more likely to respond to pembrolizumab, baseline tumor samples will be evaluated for PD-L1 expression as well as other markers using an IHC or IF assay. This work will be done retrospectively.

Furthermore, patient samples will be analyzed retrospectively for GEP scoring using the Nanostring platform.

Based on data from hundreds of patients in numerous pembrolizumab studies in multiple cancer types, these biomarkers may potentially be predictive of patient benefiting from adjuvant pembrolizumab. The purpose of this trial is to assess whether potential benefit from adjuvant therapy is also related to PD-L1 and/or GEP biomarkers.

A key question of this study is whether IDO inhibition combined with PD-1 inhibition is more effective in PD-L1 expressing / GEP positive tumors or whether this combination is able to overcome the less inflamed phenotype and lead to a response in PD-L1 negative/GEP low patients.

## 4.3 Benefit/Risk

### 4.3.1.1 Risk from Epacadostat

In 28-day toxicology studies,  $C_{max}$  values have exceeded the  $IC_{50}$  for the IDO1 enzyme in cells (7 nM) by up to 370-fold, and the  $IC_{50}$  for the vasopressin 1a receptor by up to 40-fold (130-fold in single dose studies) in the absence of any toxicity, so the risk of unintended pharmacological activity is expected to be low. In the Phase 1 clinical study in subjects with refractory solid tumors (INCB 24360-101) doses up to 700 mg BID were given without an MTD determined. Epacadostat was well tolerated with a single SAE of exacerbated radiation pneumonitis in a subject with metastases treated at 300 mg BID, 1

report of asymptomatic and reversible hypopituitarism despite continued administration of epacadostat, and 1 event of Grade 3 fatigue determined by the investigator to be related to study drug and considered a DLT in the 400 mg BID dose group.

Theoretically, inhibition of IDO1 could cause an increase in serotonin levels that could precipitate a cluster of AEs termed serotonin syndrome (SS) when administered in combination with other serotonergic agents. This rare syndrome has been associated with some monoamine oxidase inhibitors (MAOIs) and combinations of serotonergic drugs [53]. The clinical manifestations of SS range from barely perceptible to lethal; onset is rapid (within 12 hours of drug(s) administration). Based on preliminary studies in the rat, concentrations of epacadostat in the cerebrospinal fluid were below the quantifiable limit of detection (2 nM) after IV dosing, and total brain homogenate concentrations were approximately 15% of corresponding plasma concentrations. Therefore, epacadostat exhibits apparent limited penetration across the blood- brain barrier and is likely not associated with significant effects on tryptophan metabolism in the brain that might impact brain serotonin levels. This represents a hypothetical risk only and has not been observed in any clinical studies of epacadostat with over 600 subjects treated to date. Twelve subjects in the INCB 24360-201 combination study with ipilimumab were receiving concomitant treatment with an SSRI without any consequences. Although the risk is theoretical, use of MAOIs will be prohibited during the study and all subjects will be provided with an informative subject leaflet describing the signs and symptoms of the syndrome along with instructions to seek immediate medical care if any of these signs or symptoms are observed.

#### **4.3.1.2 Risk from Pembrolizumab**

An open-label Phase I study (Protocol 001) is being conducted to evaluate the safety and clinical activity of single agent pembrolizumab. The dose-escalation portion of this study evaluated 3 dose levels, 1 mg/kg, 3 mg/kg, and 10 mg/kg, administered every 2 weeks in subjects with advanced solid tumors. All 3 dose levels were well tolerated and no DLTs were observed. Based on pharmacokinetic (PK) data showing a half-life of 21 days, the Protocol was amended to include a dosing frequency of every 3 weeks in expansion cohorts. Of a total of 479 subjects, who have received pembrolizumab in Protocol 001, 466 (97.3%) experienced treatment-emergent AEs, of which 368 (76.8%) were considered drug-related. Serious AEs were reported in 30.1% of subjects, but SAEs that were attributed as potentially (possibly, probably, or definitely) drug-related by investigators were reported in 6.7% of subjects overall. Potential irAEs have been observed, including pneumonitis in both melanoma and NSCLC cohorts. The most commonly reported treatment-emergent AEs experienced have been fatigue, nausea, cough, pruritus, diarrhea, and rash. Most subjects continued treatment despite of AEs, and only 4.2% of subjects discontinued study treatment because of an AE that was considered related to study treatment by investigators. Thus, the overall AE summary suggests that pembrolizumab is generally tolerable, and AEs are generally manageable in subjects.

#### 4.3.1.3 Risk from combined Pembrolizumab and Epacadostat

The combination of pembrolizumab and epacadostat has the potential to cause more frequent, more severe, and/or new immune-related toxicities as compared with each individually.

In the ongoing Phase 1/2 study combining pembrolizumab and epacadostat, preliminary data suggest that doses up to 300 mg BID of epacadostat are well tolerated with 200 mg IV of pembrolizumab. While 300 mg bid did not exceed the MTD, there were higher rates of dose holds and reductions compared to 100 mg bid supporting 100 mg bid as the Phase 2 dose (as is detailed later in this section). In the Phase 1 portion of the study, a DLT of Grade 3 rash and Grade 3 arthralgia were seen in 2/19 evaluable subjects with epacadostat 50 mg BID; 2 DLTs out of 15 evaluable subjects were seen with epacadostat 100 mg BID cohort (Grade 3 AST and Grade 2 nervous system disorder, other - ataxia), and 4 DLTs out of 19 evaluable subjects were seen at 300 mg BID (Grade 1 erythema, 2 Grade 3 rashes and 1 nervous system disorder – other – vomiting without nausea).

The most frequently reported ( $\geq 15\%$ ) adverse events (AEs) of any grade for the combined Phase 1 and Phase 2 treatment groups (n=117) treated with epacadostat 100 mg BID were fatigue (35.0%), constipation (24.8%), diarrhea (20.5%), nausea (20.5%), vomiting (18.8%), pyrexia (16.2%) and dyspnea (15.4%). Fatigue (13.7%) and rash (11.1%) (including the preferred terms rash, rash maculopapular, rash generalized, and rash macular) were the only treatment-related AE reported in  $> 10\%$  of subjects. Treatment-related AEs of rash were only reported in the Phase 2 group.

Any Grade 3/4 AEs occurring in more than 1 subjects in the combined Phase 1 and Phase 2 epacadostat 100 mg BID group include: rash (n=5, 4.3%), dehydration (n=4 3.4%), nausea, vomiting and AST increased, (n= 3 each, 2.6%), diarrhea, small intestine obstruction, fatigue, lipase increased, hypercalcemia, hyponatremia, tumour pain, and pneumonia aspiration (n=2 each, 1.7%). Treatment-related AEs  $\geq$  Grade 3 occurring in more than one subject included rash (5 subjects, 4.3%) and dehydration, lipase increased, AST increased and nausea (2 subjects [1.7%] each).

In subjects receiving epacadostat 300 mg BID, there was an observable trend in increased adverse events of rash (total events as well as severity) and the number of required dose holds and dose reductions for epacadostat, compared to subjects receiving 100 mg BID.

Although the rashes observed at the 300 mg BID dose level were reversible with dose interruptions and medical treatment, total dose interruptions were higher in the 300 mg BID group with 5/19 interrupting epacadostat and 3 requiring dose reductions due to adverse events compared to 1 subject in 100 mg BID requiring a dose interruption, 2 subjects in 50 mg BID and 1 subject in 25 mg BID. Based on the risk for early progression during dose interruptions and dose reductions associated with epacadostat 300 mg BID in combination with pembrolizumab 200 mg IV Q3 weeks, 100 mg BID was selected as the dose for use in a proposed Phase 3 study.

Additional details regarding specific benefits and risks for subjects participating in this clinical trial may be found in the accompanying pembrolizumab and epacadostat Investigators Brochures (IBs) and Informed Consent documents.

## **5.0 METHODOLOGY**

### **5.1 Entry Criteria / Eligibility**

#### **5.1.1 Diagnosis/Condition for Entry into the Trial**

#### **5.1.2 Subject Inclusion Criteria**

In order to be eligible for participation in this trial, the subject must fulfill the following entry criteria:

1. Patients must have histologically confirmed squamous cell carcinoma of the head and neck (unresectable and not amenable to curative intent therapy)
2. Meet criteria for either the Acquired Resistance OR the Suboptimal Benefit Cohort
  - a. **Acquired Resistance is defined as (i and ii must both be met):**
    - i. **Prior *benefit* from anti-PD-1/PD-L1 therapy defined as a) prior response, *and/or* b)  $\geq 5$  months of stable disease (SD). Intervening therapies are allowed.**
    - ii. **Progressive Disease (PD) on recent scans**
  - b. **Suboptimal Benefit is defined as (i and ii must both be met):**
    - i. **Prolonged stable disease  $\geq 5$  months OR Suboptimal response ( $>10\%$  &  $<50\%$  shrinkage per RECIST at any evaluation timepoint)**
    - ii. **Ongoing stable disease on recent scans**
    - iii. **Last treatment with an anti-PD-1/PD-L1 agent within 6 weeks prior to starting protocol treatment**
3. Archival tissue for PD-L1 staining (alternatively a new biopsy (core) at baseline can be used). A minimum of 10 slides is required (unless approval from the PI is obtained)
4. Measurable disease per RECIST 1.1.
5. Known HPV status
6. ECOG performance status 0 or 1
7. Be willing and able to provide written informed consent/assent for the trial.
8. Be  $\geq 18$  years of age on day of signing informed consent.
9. Demonstrate reasonable organ function as defined in
10. Table 1, all screening labs should be performed within 10 days of treatment initiation.

**Table 1 Adequate Organ Function Laboratory Values**

System	Laboratory Value
Hematological	
Absolute neutrophil count (ANC)	≥1,500 /mcL
Platelets	≥100,000 / mcL
Hemoglobin	≥9 g/dL or ≥5.6 mmol/L without transfusion or EPO dependency (within 7 days of assessment)
Renal	
Serum creatinine OR Measured or calculated a creatinine clearance (GFR can also be used in place of creatinine or CrCl)	≤1.5 X upper limit of normal (ULN) OR  ≥40 mL/min for subject with creatinine levels > 2.0 X institutional ULN
Hepatic	
Serum total bilirubin	≤ 1.2 X ULN OR in case of Gilbert's disease an elevated total Bilirubin is allowed if direct Bilirubin is <40% of total
AST (SGOT) and ALT (SGPT)	≤ 2.5 X ULN
Coagulation	
International Normalized Ratio (INR) or Prothrombin Time (PT)	≤1.5 X ULN unless subject is receiving anticoagulant therapy as long as PT or PTT is within therapeutic range of intended use of anticoagulants
Activated Partial Thromboplastin Time (aPTT)	≤1.5 X ULN unless subject is receiving anticoagulant therapy as long as PT or PTT is within therapeutic range of intended use of anticoagulants
a Creatinine clearance should be calculated per institutional standard.	

11. Female subject of childbearing potential should have a negative urine or serum pregnancy test within 72 hours prior to receiving the first dose of study medication. If the urine test is positive or cannot be confirmed as negative, a serum pregnancy test will be required.
12. Female subjects of childbearing potential should be willing to use 2 methods of birth control or be surgically sterile, or abstain from heterosexual activity for the course of the study through 120 days after the last dose of study medication (Reference Section 5.7.2). Subjects of childbearing potential are those who have not been surgically sterilized or have not been free from menses for > 1 year.
13. Male subjects should agree to use an adequate method of contraception starting with the first dose of study therapy through 120 days after the last dose of study therapy.

### 5.1.3 Subject Exclusion Criteria

The subject must be excluded from participating in the trial if the subject:

1. Is currently participating and receiving study therapy or has participated in a study of an investigational agent and received study therapy or used an investigational device within 2 weeks of the first dose of treatment.

2. Has a diagnosis of immunodeficiency or is receiving systemic steroid therapy or any other form of immunosuppressive therapy within 7 days prior to the first dose of trial treatment.
3. Has a known history of active TB (Bacillus Tuberculosis)
4. Has hypersensitivity to pembrolizumab, epacadostat or any of its excipients.
5. Has had a prior anti-cancer monoclonal antibody (mAb) within 3 weeks prior to study Day 1, or targeted small molecule therapy within 2 weeks prior to study Day 1, or who has not recovered (i.e.,  $\leq$  Grade 1 or at baseline) from adverse events due to agents administered more than 4 weeks earlier.
6. Has not recovered from prior surgery, chemotherapy or radiation therapy from adverse events due to a previous treatment/ administered agent (i.e.,  $\leq$  Grade 1 or return to baseline prior to treatment).
  - Note: Subjects with  $\leq$  Grade 2 neuropathy, any grade hearing loss or tinnitus, or typical side effects from radiotherapy are an exception to this criterion and may qualify for the study.
  - Note: If subject received major surgery, they must have recovered adequately from the toxicity and/or complications from the intervention prior to starting therapy.
7. Has a known additional malignancy that is progressing or requires active treatment. Exceptions include basal cell carcinoma of the skin or squamous cell carcinoma of the skin that has undergone potentially curative therapy or in situ cervical cancer or any tumors that are not likely to influence live expectancy in the subsequent 3 years without active treatment (e.g. low grade prostate cancer in absence of therapy).
8. Has known active (=growing) central nervous system (CNS) metastases and/or carcinomatous meningitis. Radiation or resected brain metastasis are acceptable if clinically stable.
9. Has active autoimmune disease that has required systemic treatment in the past 2 years (i.e. with use of disease modifying agents, corticosteroids or immunosuppressive drugs). Replacement therapy (eg., thyroxine, insulin, or physiologic corticosteroid replacement therapy for adrenal or pituitary insufficiency, etc.) is not considered a form of systemic treatment.
10. Has known history of, or any evidence of active, non-infectious pneumonitis.
11. Warfarin use, even if low dose warfarin is not acceptable. However, other anti-coagulants (e.g. aspirin, enoxaparin and heparin derivatives, thrombin inhibitors, etc) are acceptable.

12. Has a history or current evidence of any condition, therapy, or laboratory abnormality that might confound the results of the trial, interfere with the subject's participation for the full duration of the trial, or is not in the best interest of the subject to participate, in the opinion of the treating investigator.
13. Has known psychiatric or substance abuse disorders that would interfere with cooperation with the requirements of the trial.
14. Is pregnant or breastfeeding, or expecting to conceive or father children within the projected duration of the trial, starting with the pre-screening or screening visit through 120 days after the last dose of trial treatment.
15. Has received prior therapy with an IDO inhibiting agent.
16. Has a known history of Human Immunodeficiency Virus (HIV) (HIV 1/2 antibodies).
17. Has known active Hepatitis B (e.g., HBsAg reactive) or Hepatitis C (e.g., HCV RNA [qualitative] is detected).
18. Has received a live vaccine within 30 days of planned start of study therapy.
19. Subjects receiving MAO-inhibitors (MAOI) or drug which has significant MAOI activity (meperidine, linezolid, methylene blue) within the 21 days before screening.
20. Any history of Serotonin Syndrome after receiving serotonergic drugs.
21. History or presence of an abnormal electrocardiogram (ECG) that, in the investigator's opinion, is clinically meaningful. Screening QTc interval > 470 milliseconds is excluded. In the event that a single QTc is > 470 milliseconds, the subject may enroll if the average QTc for the 3 ECGs is < 470 milliseconds. For subjects with an intraventricular conduction delay (QRS interval > 120 milliseconds), the JTc interval may be used in place of the QTc with sponsor approval. The JTc must be < 340 milliseconds if JTc is used in place of the QTc. Subjects with left bundle branch block are excluded.  
**Note:** QTc prolongation due to pacemaker may enroll if the JTc is normal.
22. Use of any UGT1A9 inhibitor from screening through follow-up period, including the following: diclofenac, imipramine, ketoconazole, mefenamic acid, and probenecid. See [Section 5.11](#) for more details.
23. History of organ transplant that requires use of immunosuppressives.
24. Any condition that would jeopardize the safety of the subject or compliance with the Protocol.
25. Clinically significant cardiac disease, including unstable angina, acute myocardial infarction within 6 months from Day 1 of study drug administration, New York Heart Association Class III or IV congestive heart failure, and arrhythmia requiring therapy

*Note: Seasonal influenza vaccines for injection are generally inactivated flu vaccines and are allowed; however intranasal influenza vaccines (e.g., Flu-Mist®) are live attenuated vaccines, and are not allowed within 30 days prior to initiation of treatment.*

## 5.2 Trial Treatments

The treatment to be used in this trial is outlined below in Table 2

**Table 2 Trial Treatment**

Drug	Dose/Potency	Dose Frequency	Route of Administration	Regimen/Treatment Period	Use
Pembrolizumab	200 mg mg/kg	Q3W	IV infusion	Day 1 of each 3 week cycle	Experimental
Epacadostat	100mg	Daily, BID	PO	continuous	Experimental

**Treatment Period:** Both Epacadostat and Pembrolizumab are given concurrently.

Trial treatment should initiate as soon as PD-L1 status and cohort allocation are known

### 5.2.1 Dose Selection

The rationale for selection of doses to be used in this trial is provided in Section 4.0 – Background and Rationale.

Details on preparation and administration of pembrolizumab (MK-3475) and Epacadostat are provided in the respective Pharmacy Manuals.

## 5.3 Dose Modifications

Adverse events (both non-serious and serious) associated with pembrolizumab and epacadostat exposure may represent an immunologic etiology. These adverse events may occur shortly after the first dose or several months after the last dose of treatment. Pembrolizumab must be withheld for drug-related toxicities and severe or life-threatening AEs as per Table 3 below. See below for supportive care guidelines, including use of corticosteroids.

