**Table 3: Dose Modification Guidelines for Drug-Related Adverse Events for Pembrolizumab and Epacadostat**

Toxicity	Hold Treatment For Grade	Agent	Timing for Restarting Treatment	Dose Level for	Treatment Discontinuation
Diarrhea/Colitis	2-3	Pembrolizumab	Toxicity resolves to Grade 0-1	n/a	Toxicity does not resolve within 12 weeks of last dose or inability to reduce corticosteroid to 10 mg or less of prednisone or equivalent per day within 12 weeks

		Epacadostat	Toxicity resolves to Grade 0-1	Related: Reduce by 1 dose level Not Related: Same dose level	Toxicity does not resolve within 12 weeks of last dose or inability to reduce corticosteroid to 10 mg or less of prednisone or equivalent per day within 12 weeks
	4	Pembrolizu mab	Permanently discontinue	n/a	Permanently discontinue
		Epacadostat	Permanently discontinue	n/a	Permanently discontinue
AST, ALT, or Increased Bilirubin	2	Pembrolizu mab	Toxicity resolves to Grade 0-1	n/a	Toxicity does not resolve within 12 weeks of
		Epacadostat	Toxicity resolves to Grade 0-1	Related: Reduce by 1 dose level Not Related: Same dose level	Toxicity does not resolve within 12 weeks of last dose
	3-4	Pembrolizu mab	Permanently discontinue	n/a	Permanently discontinue
		Epacadostat	Permanently discontinue	n/a	Permanently discontinue
Type 1 diabetes mellitus (if new onset) or Hyperglycemia	T1DM or 3-4	Pembrolizu mab	Hold pembrolizumab for new onset Type 1 diabetes mellitus or Grade 3-4 hyperglycemia associated with evidence of beta cell failure	n/a	Resume pembrolizumab when subjects are clinically and metabolically stable
		Epacadostat	Toxicity resolves to Grade 0-1	Related: Reduce by 1 dose level Not Related: Same dose level	Resume epacadostat when subjects are clinically and metabolically stable

Dosing interruptions are permitted in the case of medical / surgical events or logistical reasons not related to study therapy (e.g., elective surgery, unrelated medical events, patient vacation, and/or holidays). Subjects should be placed back on study therapy within 3 weeks of the scheduled interruption, unless otherwise discussed with the PI. The reason for interruption should be documented in the patient's study record.

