### 5.3.1 Criteria and Procedures for Treatment Interruption

In some circumstances, it may be necessary to temporarily interrupt both study treatments as a result of AEs that may have an unclear relationship to study drug. Any interruptions of > 2 weeks or for LFT abnormalities must be discussed with the medical monitor before resuming

treatment. Treatment with both study drugs should be withheld for drug-related Grade 4 hematologic toxicities, nonhematological toxicity  $\geq$  Grade 3 (including laboratory abnormalities), and severe or life-threatening AEs (see Table 3). Table 3 summarizes the dosing actions for MK-3475 and INCB024360 that must be implemented with the indicated related AEs. Additional information related to dose changes for INCB024360 and MK-3475 can be found in subsequent Sections.

Except in cases of emergency, it is recommended that the investigator consult with the sponsor's medical monitor (or other representative of the sponsor) before temporarily interrupting therapy for reasons other than Protocol-mandated medication hold. Additionally, the investigator must notify the sponsor's medical monitor and study project manager via email before restarting study drug that was temporarily interrupted because of an AE.

Dosing interruptions are permitted in the case of medical / surgical events or logistical reasons not related to study therapy (e.g, elective surgery, unrelated medical events, subject vacation, and/or holidays). Subjects should be placed back on study therapy within 3 weeks of the scheduled interruption, unless otherwise discussed with the sponsor. The reason for interruption should be documented in the subject's study record.

In case toxicity does not resolve to Grade 0 to 1 within 12 weeks after last infusion of MK-3475, study treatment should be discontinued after consultation with the sponsor. With investigator and sponsor agreement, subjects with a laboratory AE still at Grade 2 after 12 weeks may continue treatment in the study only if asymptomatic and controlled. For information on the management of irAEs, see below/next sections.

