#### **Table 4: General Approach to Handling Immune-Related Adverse Events**

irAE	Withhold/Discontinue Pembrolizumab (MK-3475) and Epacadostat	Supportive Care
Grade 1	No action.	Provide symptomatic treatment.
Grade 2	May withhold MK-3475 and INCB024360. Subjects with intolerable or persistent Grade 2 drug-related AE may hold study medication at physician's discretion. Permanently discontinue study drug for persistent Grade 2 AEs for which treatment with study drug has been held, that do not recover to Grade 0 to 1 within 12 weeks of the last dose.	Consider systemic corticosteroids in addition to appropriate symptomatic treatment.
Grade 3 or severe	Withhold MK-3475 and INCB024360. Discontinue if unable to reduce corticosteroid dose to < 10 mg/day prednisone equivalent within 12 weeks of toxicity or permanently discontinue for any severe or ≥ Grade 3 drug-related AE that recurs or any life-threatening event.  For grade 3 rash, dose interruption and topical treatment (see next column) until resolution are recommended. Resume at same dose although dose reduction in cases of persistent rash can be considered.	Systemic corticosteroids are indicated in addition to appropriate symptomatic treatment.  Topical steroids per physician choice (e.g. hydrocortisone, or stronger). Typically oral steroids are not required.
Grade 4	Permanently discontinue	Systemic corticosteroids are indicated in addition to appropriate symptomatic treatment.

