## **5.7 Rescue Medications & Supportive Care**

### **5.7.1 Supportive Care Guidelines**

Subjects should receive appropriate supportive care measures as deemed necessary by the treating investigator. Suggested supportive care measures for the management of adverse events with potential immunologic etiology are outlined below and in greater detail in the ECI guidance document. Where appropriate, these guidelines include the use of oral or intravenous treatment with corticosteroids as well as additional anti-inflammatory agents if symptoms do not improve with administration of corticosteroids. Note that several courses of steroid tapering may be necessary as symptoms may worsen when the steroid dose is decreased. For each disorder, attempts should be made to rule out other causes such as metastatic disease or bacterial or viral infection, which might require additional supportive care. The treatment guidelines are intended to be applied when the investigator determines the events to be related to pembrolizumab.

Note: if after the evaluation the event is determined not to be related, the investigator is instructed to follow the ECI reporting guidance but does not need to follow the treatment

guidance (as outlined in the ECI guidance document). Refer to Section 5.2.1 for dose modification.

It may be necessary to perform conditional procedures such as bronchoscopy, endoscopy, or skin photography as part of evaluation of the event. Suggested conditional procedures, as appropriate, can be found in the ECI guidance document.

- **Pneumonitis:**

- For **Grade 2 events**, treat with systemic corticosteroids. When symptoms improve to Grade 1 or less, steroid taper should be started and continued over no less than 4 weeks.
- For **Grade 3-4 events**, immediately treat with intravenous steroids. Administer additional anti-inflammatory measures, as needed.
- Add prophylactic antibiotics for opportunistic infections in the case of prolonged steroid administration.

- **Diarrhea/Colitis:**

Subjects should be carefully monitored for signs and symptoms of enterocolitis (such as diarrhea, abdominal pain, blood or mucus in stool, with or without fever) and of bowel perforation (such as peritoneal signs and ileus).

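### Grade 2 pneumonitis, hypophysitis and nephritis are treated with corticosteroids but have no required hold, and Tables 3 and 4 conflict where they overlap

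*Combined protocol and SAP*

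**What the plan says.** Section 5.3 ties withholding of pembrolizumab to Table 3: "Pembrolizumab must be withheld for drug-related toxicities and severe or life-threatening AEs as per Table 3 below". Section 5.3.1 extends this to both agents: "Table 3 summarizes the dosing actions for MK-3475 and INCB024360 that must be implemented with the indicated related AEs". The table's title is general, "Table 3: Dose Modification Guidelines for Drug-Related Adverse Events for Pembrolizumab and Epacadostat", but it has three toxicity groups: "Diarrhea/Colitis", "AST, ALT, or Increased Bilirubin", and new-onset type 1 diabetes or hyperglycaemia.

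Section 5.3.1 adds a general rule: both drugs are withheld for drug-related Grade 4 haematological toxicity, for non-haematological toxicity of Grade 3 or higher, and for severe or life-threatening events.

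Table 4 (section 5.3.2) covers immune-related events of any organ. At Grade 2 it says "May withhold MK-3475 and INCB024360". At Grade 3 it withholds both drugs, with conditions for discontinuation. At Grade 4 it discontinues permanently.

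Section 5.7.1 gives supportive care by event class. For Grade 2 pneumonitis the instruction is to "treat with systemic corticosteroids. When symptoms improve to Grade 1 or less, steroid taper should be started", with a minimum taper of 4 weeks. Grade 2 hypophysitis and nephritis are also treated with corticosteroids. For dose modification, 5.7.1 sends the reader to section 5.2.1.

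**The concern.** An investigator facing a Grade 2 lung, pituitary or kidney event finds an instruction to give corticosteroids but no required action on the study drugs. For a Grade 2 bowel or liver event, Table 3 requires both drugs to be held. The documents do not explain the difference.

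The protocol itself treats pneumonitis as a known risk. Exclusion criterion 10 bars a patient who "Has known history of, or any evidence of active, non-infectious pneumonitis", and section 4.3.1.2 reports pneumonitis among the potential immune-related events seen with pembrolizumab.

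What is at stake is mainly patient safety: the rules as written allow both drugs to be given through an active Grade 2 event of these kinds. A second issue is consistent conduct. Where two tables give different actions for the same event and grade, two investigators can each follow the protocol and act differently.

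**Working it through.** The plan states no figure on this point, so the check compares the sections directly.

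**Step 1: event classes.** Section 5.7.1 manages eight: pneumonitis, diarrhoea/colitis, type 1 diabetes/hyperglycaemia, hypophysitis, thyroid disorders, hepatic events, renal failure/nephritis and infusion reactions. Table 3 covers three and Table 5 covers infusion reactions. 8 − 3 − 1 = 4 have no event-specific dosing action: pneumonitis, hypophysitis, thyroid and renal.

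**Step 2: what applies at each grade.**

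| Event class | Table 3 | Table 4 (any immune-related event) | Section 5.3.1 general rule |
|---|---|---|---|
| Diarrhoea/colitis, Grade 2 | Hold both drugs | Hold optional | Not reached |
| AST/ALT/bilirubin, Grade 2 | Hold both drugs | Hold optional | Not reached |
| Pneumonitis, hypophysitis, nephritis, Grade 2 | No row | Hold optional | Not reached |
| AST/ALT/bilirubin, Grade 3 | Permanently discontinue both | Withhold both | Withhold both |
| Pneumonitis, hypophysitis, nephritis, Grade 3 | No row | Withhold both | Withhold both |
| Pneumonitis, hypophysitis, nephritis, Grade 4 | No row | Permanently discontinue | Withhold both |

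For the unlisted events, a hold or discontinuation is required at Grade 3 and above. Only at Grade 2 is nothing required.

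**Step 3: does another section supply a Grade 2 hold?**
- Section 5.3.2 calls for immediate discussion with the PI of any immune-related event of Grade 2 or higher. That is oversight, not a hold.
- Section 5.6.3 exempts steroids given for an event of suspected immunologic cause from its glucocorticoid prohibition, so the steroid course does not itself take the patient off treatment.
- Section 5.3.1 recommends, outside emergencies, consulting the medical monitor before an interruption that the protocol does not mandate. A Grade 2 pneumonitis hold falls under that extra step; a Grade 2 ALT hold does not.
- The section 5.7.1 reference to 5.2.1 leads to Dose Selection, which contains no modification rule.

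**Step 4: which table governs?** Rows 1, 2 and 4 above give different actions for the same event and grade. No sentence in 5.3, 5.3.1 or 5.3.2 says which table prevails.

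**The case against.** The strongest reply is that Table 3 is the specific rule and Table 4 the general one. Section 5.3.1 limits Table 3's mandatory force to the events it lists and says that further information on dose changes follows later, and Table 4 is presented as a general approach. On this reading, discretion for unlisted Grade 2 events is a deliberate clinical choice. This is a fair reading and may be the intended one. But the protocol does not state it, and it leaves unexplained why Grade 2 bowel and liver events require a hold while other Grade 2 events treated with corticosteroids do not.

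Several stronger readings are not supported:
- **That there is no instruction for a lung event, or that discussion with the PI is the only safeguard.** Section 5.3.1 and Table 4 act from Grade 3. At Grade 2 the physician may hold treatment, and Table 4 requires discontinuation if a held, persistent event has not recovered within 12 weeks of the last dose. Section 5.9 allows withdrawal by investigator decision, and section 10.10 provides weekly safety review. Sections 5.3.2 and 5.7.1 also point to a separate guidance document that is not available here.
- **That the gap can be sized by the doses falling within the 4-week taper.** The taper starts only after improvement to Grade 1 or less. Bowel and liver events carry the same minimum taper, and Table 3 lets those events restart at Grade 0-1 without waiting for it to finish. Doses in the taper are therefore permitted for listed and unlisted events alike.
- **That the steroid argument extends to thyroid events.** At Grade 2, section 5.7.1 manages these with beta-blockers or hormone replacement.
- **That the safety results would be materially distorted.** Section 8.1 summarises toxicity by type and severity, and interruption rates are not a stated outcome. The study is intended as single-centre, with Grade 2 events going to the PI, which limits variation between clinicians.

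**Conclusion.** The concern holds as a Grade 2 gap combined with an unresolved conflict between two tables. Four of the eight event classes in section 5.7.1 have no event-specific dosing action. Three of those four (pneumonitis, hypophysitis, nephritis) are treated with corticosteroids at Grade 2 while a hold remains optional. Tables 3 and 4 disagree for Grade 2 diarrhoea/colitis, Grade 2 AST/ALT/bilirubin and Grade 3 AST/ALT/bilirubin.

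The extra exposure that the gap allows is the time a patient spends at Grade 2 while still being dosed. The documents give no basis for estimating it, so no number is attached.

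The finding assumes that Table 3 is complete as read. Some of its cells are truncated in the extracted text, so it should be checked against the original PDF. There is no sign of a lost row: the text runs from the diabetes row straight to the closing paragraph, and the contents list puts 5.3 on page 31 and 5.3.1 on page 32.

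This should be corrected because it bears on patient safety and costs little. It does not affect the primary response analysis, and it implies no view on which dosing rule is clinically right.

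**What to change.** 1. Reconcile section 5.3 with Table 3, section 5.3.1, Table 4 and section 5.7.1, so that each event class in 5.7.1 has one consistent dosing action for each drug at each grade. The sponsor and investigator decide the clinical content. If discretion at Grade 2 is intended for the unlisted events, say so explicitly.
2. State in section 5.3 which table governs when an event appears in Table 3 and also falls under Table 4, and resolve the Grade 2 and Grade 3 conflicts accordingly.
3. Replace the section 5.7.1 reference to 5.2.1 with the section that holds the dose-modification rules. Section 5.9 cites 5.2.1.2, which does not exist, and can be corrected at the same time.
4. Before amending, check Table 3 against the source PDF.

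The cost is a text amendment with its IRB review. These edits add no patients, visits or tests and leave the sample size and analysis unchanged.
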